NON-INTERVENTIONAL (NI) STUDY PROTOCOL

| | |
|---|--|
| Title | Provider Referral Patterns Following Nephrectomy in High-Risk Locoregional Renal Cell Carcinoma |
| Protocol number | A6181230 |
| Protocol version identifier | Final Version 4 (Amendment 1) |
| Date | 27 March 2020 |
| Research question and objectives | To estimate the proportion of patients diagnosed with locoregional renal cell carcinoma who are at high risk for recurrence following nephrectomy, describe referral patterns, and characterize treatment in this population. Outcomes including estimation of the incidence of recurrence and disease-free interval following nephrectomy will be reported overall and among the subgroup of patients receiving adjuvant systemic therapy with sunitinib following nephrectomy. |
| Authors | 
Pfizer Inc.:
 
[REDACTED] PharmD, MSc
 
[REDACTED]
 
Duke University's School of Medicine and Health System:
 
[REDACTED] MD
 
[REDACTED]
 
RTI Health Solutions:
 
[REDACTED] MS
 
[REDACTED]
 
[REDACTED] PhD
 
[REDACTED]
 |

This document contains confidential information belonging to Pfizer. Except as otherwise agreed to in writing, by accepting or reviewing this document, you agree to hold this information in confidence and not copy or disclose it to others (except where required by applicable law) or use it for unauthorized purposes. In the event of any actual or suspected breach of this obligation, Pfizer must be promptly notified.

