8. RESEARCH QUESTION AND OBJECTIVES

The aim of this study is to estimate the proportion of patients diagnosed with RCC who are at high risk for recurrence following nephrectomy, describe referral patterns, and characterize treatment in this population. Exploratory analyses may include estimation of the incidence of recurrence and disease-free interval following nephrectomy, if data are available. Data for this study will be collected from a retrospective medical record review of patients diagnosed with locoregional RCC who underwent nephrectomy at Duke. The following primary objectives will be assessed:

- Describe patient demographic and clinical characteristics of patients diagnosed with locoregional RCC who underwent nephrectomy.
- Estimate the proportion of patients at high risk of recurrence following nephrectomy.

- Characterize postoperative provider referrals among patients at high risk of recurrence, including the proportion of patients who were referred to other providers and reasons for referral.
- Describe treatment characteristics following nephrectomy among patients at high risk of recurrence, including the proportion of patients who received systemic therapy, type of systemic therapy received, dose and duration of treatment, reasons for treatment discontinuation, and participation in clinical trials, where available; perform subgroup analyses to describe treatment details among the subgroup of patients receiving adjuvant systemic therapy with sunitinib.
- Estimate the incidence of disease recurrence and duration of the disease-free interval following nephrectomy among all patients at high risk of recurrence, and among the subgroup of patients receiving adjuvant systemic therapy with sunitinib.

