9.1.3. Part 3: Expanded Data Collection

Results from the part 2 study indicated that referral and treatment patterns show an increasing trend from 2018 into 2019. To further capture this trend, an additional sample of all patients with nephrectomies occurring through 31 December 2019 will be abstracted. The additional sample size during this period is estimated to be approximately 115-150 patients, for a full

combined sample of up to 650 patients in total. In addition, expanded follow-up data (ie, referral patterns, treatment patterns, and outcomes) will be collected for previously identified patients at high risk of recurrence, to include follow-up dates through the most recent available medical record entry prior to the abstraction date.

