9.2. Setting

Data will be abstracted from the Duke EMR system. Patients whose data will be included in the study will have met the criteria described in [Sections 9.2.1](#) and 9.2.2. Refer to [Figure 1](#) for a depiction of the follow-up period. No minimum follow-up time will be required. Outcomes among patients who are determined to be at high risk of recurrence will be observed over each patient's follow-up period—from the date of nephrectomy to death, disease recurrence, or the last date in their medical record (whichever occurs first).

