9.3.6. Outcomes (high-risk subgroup only)

Health outcomes will be collected only for patients at high risk of recurrence, when available.

- Date of last follow-up encounter in the medical record;
- Date of death;
- Date of disease recurrence and method of confirmation;
- Type of disease recurrence (eg, locoregional versus distant, if applicable);
- Reasons for treatment discontinuation.

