9.7. Data Analysis

All variables described in [Section 9.3](#) will be summarized descriptively through the tabular display of mean values, 95% confidence intervals (CIs), medians, quartiles, and standard deviations of continuous variables of interest and frequency distributions for categorical variables. All open-ended text fields associated with the “other” answer option will be evaluated and described, as appropriate.

All study-eligible patients will be included in descriptive analyses of variables pertaining to patient characteristics, baseline clinical characteristics, and initial postoperative follow-up visits (see [Sections 9.3.1](#), [9.3.2](#), and [9.3.3](#) for details). Patients who are categorized as having a high risk of recurrence will be included in additional analyses described below. Risk classification will be assessed using published algorithms (eg, UISS and SSIGN score) or adaptation of a published algorithm. The primary risk classification system used to designate the high-risk subgroup for this study will be chosen based on completeness of data available in the patient medical records. Completeness will be assessed during the pilot study. If data are available to support more than one classification system, the UISS risk classification will be used. If some data are not available to support classification using a published algorithm, an adapted version of an algorithm will be explored.

Additional descriptive analyses performed within the high-risk subgroup will include referral patterns, treatment patterns, and health outcomes (see [Sections 9.3.4](#), [9.3.5](#), [9.3.6](#)). In addition to descriptive analyses, time-to-event measures (ie, time to recurrence, overall survival) will be assessed. To adjust time-to-event measures, a Kaplan-Meier method that accounts for right-censoring will be implemented (Klein and Moeschberger, 2005).⁷ To evaluate time to recurrence, the endpoint will be programmed with the date of recurrence or date of death, whichever occurs first, as an eligible event; if neither of these events occurred, the outcome will be right censored at the date of the last medical record follow-up. To evaluate overall survival, the endpoint will be programmed with the date of death as an eligible event or right censored at the date of the last medical record follow-up.

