Exploratory semiparametric Cox proportional hazards models will be used to evaluate factors associated with time to recurrence and overall survival. These outcomes will be defined as described previously. Separate models will be estimated for time to recurrence and overall survival. The models will take the following general form:

$$h(t) = h_0(t) \exp(\beta_1 \text{DEMOGRAPHIC}_i + \beta_2 \text{CLINICAL}_i), \text{ (Equation 2)}$$

Where the following apply:

- $h(t)$ will be the hazard function of recurrence and overall survival as a function of explanatory variables.

- $h_0(t)$ will be the baseline hazard of recurrence and overall survival.
- DEMOGRAPHIC will be a vector of patient demographic characteristics, including but not limited to the following:
 - Age;
 - Sex.
- CLINICAL will be a vector of underlying clinical characteristics, including but not limited to the following:
 - Tumor histology;
 - Type and duration of systemic treatment;
 - Referral status;
 - Subsequent procedures.

The independent variables included in the final Cox proportional hazard models will be selected through an iterative process. First, separate univariate models assessing the relationship between each potential independent variable (eg, tumor histology) and the time-to-event outcome (ie, recurrence and overall survival) will be fit (Klein and Moeschberger, 2005).⁷ The model with the lowest Akaike information criteria (AIC) will be selected for further evaluation. Next, each unselected variable will be added independently to the previously selected model to determine whether the addition of the specific variable results in a lower AIC. The model with the lowest AIC will be selected for further evaluation. This process will be repeated with each of the remaining unselected variables until the addition of unselected variables no longer lowers the AIC. The most parsimonious model will have the lowest AIC. Additionally, variables of clinical significance may be included in the model. The overall goodness-of-fit of the final model will be assessed using Cox-Snell residuals and the proportional hazards assumption for the final set of covariates (Klein and Moeschberger, 2005).⁷

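### Section 9.7 calls a recurrence-or-death composite time to recurrence, and the separate objective on incidence of recurrence has no estimate at a stated time

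*Combined protocol and SAP*

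**What the plan says.** The title page states: "Outcomes including estimation of the incidence of recurrence and disease-free interval following nephrectomy will be reported overall". Section 8 includes this among its primary objectives: "Estimate the incidence of disease recurrence and duration of the disease-free interval following nephrectomy among all patients at high risk of recurrence", and asks for the same in the sunitinib subgroup. Both places treat incidence of recurrence and the disease-free interval as two quantities. The opening paragraph of Section 8 and the abstract (Section 4) nevertheless describe them as possible exploratory analyses, so their status is mixed.

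Section 9.7 says that "time-to-event measures (ie, time to recurrence, overall survival) will be assessed". For the first of these measures, "the endpoint will be programmed with the date of recurrence or date of death, whichever occurs first, as an eligible event"; patients with neither event are censored at their last medical record follow-up. The estimator is Kaplan-Meier, with no time point named. The term disease-free interval does not appear in Section 9.7, although the abstract gives it as its example of a Kaplan-Meier outcome. In the Cox model, h0(t) "will be the baseline hazard of recurrence and overall survival".

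On follow-up, Section 9.2 says: "No minimum follow-up time will be required". Section 9.1.3 adds recent operations: "an additional sample of all patients with nephrectomies occurring through 31 December 2019 will be abstracted". Section 9.3.6 collects "Date of disease recurrence and method of confirmation", with date of death as a separate item.

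**The concern.** There are two linked faults.

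**The name does not match the event.** A death with no recorded recurrence counts as an event in a result called recurrence. A report or conference abstract will carry the label without the programming rule. The Cox model has the same problem: a hazard ratio for age, which Section 9.7 lists as a covariate, would mix deaths without recurrence into what is presented as a factor associated with recurrence.

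**One objective has no matching estimate.** The composite serves the disease-free interval. Incidence of recurrence is left with the general rule that Section 9.3 variables are summarised descriptively, which gives a crude proportion of patients with a recorded recurrence. Its value depends on how long each patient happened to be observed and on how many moved to care outside Duke. It cannot be read as a risk by a given time or compared with another series. Part 3 makes this worse by adding patients with only months of possible follow-up.

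The study is descriptive, so these estimates are its product.

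**Working it through.** **The plan's own figure.** Section 9.5 expects 15%-20% of about 650 patients to be high risk: 0.15 × 650 = 97.5 (98) and 0.20 × 650 = 130. The stated 98-130 reproduces. There is no power or event calculation to check.

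**Follow-up range.** Nephrectomies run from 01 April 2014 to 31 December 2019, and expanded collection is planned for Q2 2020 (Section 6). Taking mid-May 2020 as the abstraction date, possible follow-up runs from about 0.4 to 6.1 years.

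**Assumed inputs.** The documents give no rate of death without recurrence and no loss rate. The only relapse figure is up to 40% in Section 7. It has no time horizon, and it refers to distant relapse in regional disease rather than any recurrence in the high-risk group defined here. For illustration:
- net recurrence by 5 years R = 40%
- net death without recurrence by 5 years D = 5%, 10% or 15%
- constant hazards

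**Formulas (t in months).**
- hr = -ln(1 - R)/60 = -ln(0.60)/60 = 0.00851
- hd = -ln(1 - D)/60 = 0.00085, 0.00176 or 0.00271
- Composite(t) = 1 - exp(-(hr + hd)t)
- Cumulative incidence of recurrence, CIF(t) = hr/(hr + hd) × Composite(t)

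For D = 10% at 36 months: Composite = 1 - exp(-0.01027 × 36) = 30.9%; CIF = (0.00851/0.01027) × 30.9% = 25.6%; gap 5.3 points.

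| Time | Composite, D = 5 / 10 / 15% | CIF of recurrence | Gap (points) |
|---|---|---|---|
| 1 year | 10.6 / 11.6 / 12.6% | 9.7 / 9.6 / 9.6% | 1.0 / 2.0 / 3.0 |
| 2 years | 20.1 / 21.8 / 23.6% | 18.3 / 18.1 / 17.9% | 1.8 / 3.7 / 5.7 |
| 3 years | 28.6 / 30.9 / 33.2% | 26.0 / 25.6 / 25.2% | 2.6 / 5.3 / 8.0 |

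With R between 30% and 50%, the 3-year gap is 2.5-8.4 points. At R = 40%, the share of composite events that are deaths is hd/(hr + hd) = 9.1%, 17.1% or 24.1%.

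**Crude proportion.** With f the months from nephrectomy to mid-May 2020 and H = hr + hd + loss hazard, the crude proportion is the average over patients of (hr/H) × (1 - exp(-Hf)).

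| Accrual and loss | Crude proportion | Against the 3-year CIF |
|---|---|---|
| Even accrual, no loss | 25.7-26.7% | 0.4-0.7 points above |
| Even accrual, 10-20% loss per year | 18.0-22.3% | about 3.8-7.5 points below |
| Section 9.1.3 counts (115-150 of 650 in Part 3), no loss | 23.5-25.7% | about 0.3-1.7 points below |
| Section 9.1.3 counts, 10-20% loss per year | not tabulated | about 4.5-8.8 points below |

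The near-agreement with no loss is an accident of this follow-up mix. The same hazards give 28.4-29.6% for the Part 2 dates (April 2014 to March 2019) and about 7.3% for April to December 2019.

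**Scale.** The 95% half-width for a proportion of 25% is 1.96 × sqrt(0.25 × 0.75/n) = 8.6 points at n = 98 and 7.4 points at n = 130.

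**The case against.** The strongest reply is that nothing is hidden. Section 9.7 states the event and the censoring rule in full, and the Cox section says its outcomes keep those definitions, so a programmer would build the intended endpoint. Read with the abstract, the composite is naturally the disease-free interval analysis. Recurrences would be counted in the descriptive tables. The study tests no hypothesis, and Section 8 partly calls this work exploratory. The numerical gaps rest on assumed rates, are no larger than about one confidence-interval half-width, and for the crude proportion become large only if substantial loss is assumed. The choice of 1, 2 and 3 years and of Aalen-Johansen is one reasonable option among several, and the 3-year estimate would be thin.

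Much of this is fair. The composite is legitimate and should stay, only the direction of its difference from recurrence incidence is certain, and the exact landmarks are open to choice. But the same reading leaves incidence of recurrence with no defined estimate. Carrying the definition into the Cox model carries the wrong name with it. Sampling error is no defence either, because the mislabelling acts in one direction and an interval around the composite does not address the recurrence objective.

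**Conclusion.** The concern holds on the text. If Section 9.7 is followed as written, deaths without recorded recurrence are reported under the name of recurrence, and a separately listed objective is answered only by a crude proportion over unequal follow-up. It is certain that the composite is at or above the cumulative incidence of recurrence. The size is not known: it is about 1-3 points at 1 year and 2.6-8.0 points at 3 years if net 5-year recurrence is 40%, net 5-year death without recurrence is 5-15%, and hazards are constant. The crude proportion could lie slightly above or well below the 3-year risk, depending on accrual and loss. This affects interpretation only, with no change to sample size or error rates. It should be corrected before the expanded analysis is reported.

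**What to change.** In Section 9.7:

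1. Rename the composite *disease-free survival (first of recurrence or death)*, state that it answers the disease-free interval objective, and keep its Kaplan-Meier method and censoring rule.
2. Define incidence of recurrence as the Aalen-Johansen cumulative incidence at 1, 2 and 3 years, with 95% CIs and numbers at risk. Recurrence is the event, death without recorded recurrence is the competing event, and censoring is at the last medical record follow-up. Report it for all high-risk patients and, where numbers allow, for the sunitinib subgroup. If the crude proportion is also shown, label it as recorded recurrence during observed follow-up and give the median follow-up.
3. Relabel the Cox model and its h(t) and h0(t) as disease-free survival. A cause-specific recurrence model is an optional sensitivity analysis.
4. Present the composite and the cumulative incidence side by side. State that care outside Duke may be unseen (Section 9.9), so some deaths may follow unrecorded recurrences and the cumulative incidence may be too low.

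The cost is wording and a little more SAS work. Recurrence and death dates are already separate items in Section 9.3.6, so no new abstraction is needed. The main limit is precision: in the illustration, about 31-50 of the 98-130 patients remain at risk at 3 years with no loss, and 16-37 with 10-20% loss per year. The sunitinib estimate may be imprecise, and its time origin must be stated, because a patient has to be recurrence-free to start adjuvant therapy.

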9. RESEARCH METHODS

To achieve the study objectives, retrospective medical record data of adult patients diagnosed with locoregional RCC who received a nephrectomy at Duke will be compiled by Duke researchers and analyzed by RTI Health Solutions (RTI-HS) analysts. RTI-HS will develop a customized data-collection form (DCF) to capture detailed information on patient demographics, clinical characteristics, health outcomes, treatments, and postoperative referrals from the medical records of eligible patients. Patients will be selected based on specific inclusion and exclusion criteria described in [Sections 9.2.1](#) and [9.2.2](#). All necessary study materials will be submitted to Duke's institutional review board (IRB) for review and RTI International's¹ IRB for study classification.

Following receipt of each IRB's classification or approval of the study (where required), Duke researchers will proceed with implementation of the pilot study (pilot phase). The pilot phase will consist of a pilot study to assess whether an adequate sample of the patient population of interest is available, evaluate the quality and completeness of available data, and quantify the duration of follow-up care available in Duke's electronic medical record (EMR) system. Using lessons learned from the pilot study, part 2 (the full study) will consist of abstracting data for a large sample of patients, analyzing the data, and preparing a study report and other materials for disseminating the study findings (ie, conference abstract, poster, and manuscript). Based on the temporal trends observed in part 2, the data abstraction will be expanded to include part 3 (the expanded study), which will consist of abstracting data on the additional patients who underwent nephrectomy through 2019 and expanded follow-up data collection (ie, referral patterns, treatment patterns, and outcomes) for previously identified patients at high risk of recurrence, to include follow-up dates through the most recent available medical record entry prior to the abstraction date.

[figure not shown]
¹ RTI Health Solutions is a business unit of the not-for-profit research organization RTI International.

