9.1. Study Design

This study is a retrospective, observational medical record review of patients diagnosed with locoregional RCC who received a nephrectomy at Duke between 01 April 2014 and 31 December 2019. The date of the nephrectomy will be considered the *index date*.

Background clinical characteristics such as date of initial and locoregional RCC diagnoses will be identified during the period prior to the index date. Recurrence risk status will be assigned at the index date, using information available in the record at or around the index date. During the follow-up period (ie, the period between the index date and the last entry in the medical record, death, or disease recurrence), outcomes including treatment, referrals, and disease recurrence will be assessed for patients who were determined to have been at high risk of recurrence following their nephrectomy, where data are available. Figure 1 provides a visual schematic of relevant observation periods.

Figure 1. Patient Observation Periods

RCC = renal cell carcinoma.

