Cox proportional hazards models will generate a hazard ratio for each of the covariates included in the model, indicating the higher or lower rate of an event (relative to a reference category) at any given point in time following nephrectomy. Like odds ratios from a logistic model, a hazard ratio less than 1 indicates a lower rate of an event, while a ratio greater than 1 indicates a higher rate of an event, relative to a reference category.

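### The exploratory Cox models start at nephrectomy but use referral, systemic treatment and later procedures as covariates with no timing rule, so null exposures can give hazard ratios well below or above 1

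*Combined protocol and SAP*

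**What the plan says.** Section 9.1 makes the date of nephrectomy the index date. Section 9.7 explains each Cox HR as "indicating the higher or lower rate of an event (relative to a reference category) at any given point in time following nephrectomy", so the time scale is time since surgery.

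Equation 2 in Section 9.7 carries a patient subscript on its covariates and no time argument. Its text states that "CLINICAL will be a vector of underlying clinical characteristics". The examples listed include "Type and duration of systemic treatment", referral status and "Subsequent procedures". The same list serves the models for time to recurrence (recurrence or death, whichever is first) and overall survival. Covariates enter by forward selection on AIC.

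The sections differ on where observation ends:

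- Section 9.1 defines follow-up as "the period between the index date and the last entry in the medical record, death, or disease recurrence", and Section 9.2 says the same, taking whichever comes first.
- Section 9 announces "expanded follow-up data collection (ie, referral patterns, treatment patterns, and outcomes) for previously identified patients at high risk of recurrence", and Section 9.1.3 extends this "to include follow-up dates through the most recent available medical record entry prior to the abstraction date". Neither names recurrence as a stopping point.
- The overall survival endpoint in Section 9.7 runs to death or the last record, which requires follow-up past recurrence.

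**The concern.** Nobody has a referral, a treatment duration or a later procedure at time zero. If a patient is coded from the start of follow-up by what happened later, two errors follow.

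- **Exposures stop counting at recurrence.** A patient must remain event-free long enough to be referred, to start treatment or to build up duration. Patients who recur first are coded unexposed. This immortal time pushes the HR below 1.
- **Exposures after recurrence count.** Recurrence itself can prompt a referral, systemic therapy or a procedure. The event then causes the exposure, which pushes the HR up, possibly above 1.

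Two analysts could follow the plan and report opposite associations from the same records. Referral and treatment are the study's subject, and Section 9 foresees an abstract, a poster and a manuscript. A referral with no effect could be published as linked to fewer, or to more, recurrences. Confounding by indication is a separate problem.

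**Working it through.** **The plan's own figure.** Section 9.5 expects 15%-20% of about 650 patients to be high risk: 0.15 × 650 = 97.5 (98) and 0.20 × 650 = 130. This reproduces. The checks below use n = 115, about the midpoint.

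**Inputs.** The documents give no timing for referral or treatment. Section 7 gives relapse of up to 40% with no time horizon. The assumptions are therefore: 40%-50% with an event at 5 years at constant hazard; follow-up of 4.5-73 months; 50% of patients destined for referral, with exponential delay of median 1, 3, 6 or 12 months; and no effect of referral (true HR = 1). At n = 115 this gives 31-40 events.

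**Mechanism by hand.** The event hazard is λ = −ln(1 − p)/60, so 0.0085 per month for p = 0.40 and 0.0116 for p = 0.50. The referral rate is μ = ln 2/median delay. Ignoring censoring, a patient destined for referral has the event first with probability λ/(λ + μ):

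- 1 month (μ = 0.693): 1.2%-1.6%
- 3 months (μ = 0.231): 3.6%-4.8%
- 6 months (μ = 0.116): 6.9%-9.1%
- 12 months (μ = 0.058): 12.8%-16.7%

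Under fixed coding, every one of these patients moves to the unreferred group, and every one is an event.

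**Time-to-recurrence HR under the null, fixed coding** (400,000 simulated patients per scenario):

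| Median delay | Exposures stop at recurrence | 25% of recurrences trigger a counted referral | 50% trigger |
|---|---|---|---|
| 1 month | 0.91-0.92 | 1.36-1.42 | 2.2-2.3 |
| 3 months | 0.78-0.79 | 1.22-1.28 | 2.0-2.1 |
| 6 months | 0.66-0.67 | 1.09-1.14 | 1.8-2.0 |
| 12 months | 0.56-0.57 | 1.04-1.07 | 1.8-1.9 |

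The HR crosses 1 once about 5%, 12%-14%, 19%-20% or 22%-24% of recurrences trigger a counted referral, at the four delays in order. Time-dependent coding gave 0.99-1.01, as did 3- and 6-month landmarks.

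**Different assumptions.** A second simulation (5-year recurrence of 40% or 60%, separate death hazards, censoring at 3-72 months) gave HRs of about 0.8-0.9 for pre-event exposure at a median of 1-2 months and 0.53-0.63 at 6-12 months. With 70% newly exposed after recurrence it gave 2.2-2.6. A further run with death in the composite event gave about 0.55-0.97 with no trigger, 1.0-1.5 at 25% and 1.7-2.2 at 50%.

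**Treatment duration as a fixed covariate.** Assume untreated patients are set to 0, start is at a median of 1.5-3 months, planned duration has mean 6-12 months capped at 12-24, and duration stops at the event. The HR is then 0.79-0.87 per 6 months if 30% are treated. Cumulative exposure to date gave 0.98-1.02.

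**Forward AIC selection, n = 115.** A null referral covariate was kept in 16%-21%, 28%-29%, 36%-47% and 56%-63% of datasets at the four delays with no trigger, and in 65%-78% with a 50% trigger. Time-dependent coding kept it in 13%-19%. Monte Carlo error is about 4-6 points.

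**Overall survival.** Assume median survival after recurrence of 24-36 months and 5% other-cause death over 5 years. Fixed coding gave 0.50-0.91 (no trigger), 0.80-1.21 (25%) and 1.16-1.71 (50%). Time-dependent coding alone did not repair this: 0.68-0.94, 1.15-1.33 and 1.76-2.12. Adding a time-dependent recurrence indicator gave 0.97-1.02. A 3- or 6-month landmark among patients alive and recurrence-free gave 0.94-1.03.

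**The case against.** **Fixed coding is not stated.** Equation 2 is offered as a general form with loose notation, so the plan can be called silent. That is fair as far as it goes. But the text calls these variables underlying characteristics and gives no other rule, and total treatment duration cannot be known at nephrectomy under any reading.

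**Exposures after recurrence may not be meant to count.** The extension in Sections 9 and 9.1.3 can be read as lifting a calendar limit, still subject to the stop at recurrence in Sections 9.1 and 9.2. Section 9.3.5 dates adjuvant therapy specifically. On that reading HRs above 1 do not arise for time to recurrence, but the bias below 1 remains. Section 9.3.5 also collects systemic agents without that limit, and overall survival still needs follow-up past recurrence.

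**The sizes rest on assumed inputs.** This stands. Section 9.3.3 records a plan at the first postoperative visit, so some decisions may be early. At a 1-month delay with nothing counted after recurrence, the bias is small and the AIC result cannot be told apart from that under correct coding.

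**Overall survival has few deaths.** Under these assumptions there would be about 14-21 deaths among 115 patients, too few for many covariates plus a recurrence indicator. This limits what that model can carry. It does not rescue fixed coding.

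**The models are exploratory.** They run only if the sample is sufficient (Section 9.1.2), Section 9.5 disclaims formal testing, and no objective in Section 8 needs a covariate HR. This limits the seriousness, but an exploratory label does not warn a reader of a structural bias.

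**Conclusion.** The concern holds. Read as written, the plan produces HRs for referral, systemic treatment and later procedures that depart from 1 with no true effect, and it does not settle the direction. The mechanism follows from the time origin and the covariate list. The size depends on assumed timing: from about 0.9 for exposure within a month with nothing counted after recurrence, to roughly 0.56 for late exposure, and to about 2 when half of recurrences lead to a counted exposure. With few triggered exposures the two biases can nearly cancel. The descriptive results and the Kaplan-Meier estimates for the whole high-risk group do not use these covariates and are unaffected. This should be fixed before the Cox models are run or reported.

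**What to change.** Amend Section 9.7 as follows:

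1. Enter referral, start of systemic therapy (by type) and subsequent procedures as time-dependent covariates: 0 until the recorded day and 1 afterwards, with counting-process input. Alternatively, use a prespecified landmark day.
2. Remove total treatment duration as a fixed covariate, or replace it with cumulative exposure to date.
3. In the time-to-recurrence model, count only exposures dated before the event.
4. For overall survival, state whether exposures after recurrence count, and add a rule for recurrence itself: a landmark among patients alive and recurrence-free, or a time-dependent recurrence indicator. Keep the covariate list short, given the likely number of deaths.
5. Reconcile Sections 9.1 and 9.2 with Sections 9, 9.1.3 and 9.7 on follow-up past recurrence.

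The cost is SAP wording and slightly more programming. Sections 9.3.4 and 9.3.5 already collect referral, procedure and adjuvant-therapy dates. Section 10 keeps day differences for study endpoints; one line should confirm that this covers days from index to referral, treatment start and stop, and procedures.

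Time-dependent coding drops no patients. A 3-month landmark loses to early events 115 × (1 − 0.6^(3/60)) = 2.9 to 115 × (1 − 0.5^(3/60)) = 3.9 patients. A 6-month landmark loses 115 × (1 − 0.6^(6/60)) = 5.7 to 115 × (1 − 0.5^(6/60)) = 7.7, plus 2-3 censored earlier. Losses could be larger, because Section 9.2 sets no minimum follow-up and Section 9.3.3 allows transfer to outside providers. A recurrence indicator removes any survival effect that works by preventing recurrence; the landmark does not. None of these steps removes confounding by indication, and the report should say so.
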